8.1 Subgroup Analyses

No subgroup efficacy analyses will be performed.

9 Safety Analyses

Safety analysis will be performed using the safety analysis set. Baseline is defined as the last data obtained prior to initiation of IMP treatment in this trial.

9.1 Extent of Exposure

Descriptive statistics and frequency distribution (1-7, 8-14, 15-21, 22-28, 29-35, 36-42, 43-49, 50-56, 57-63, 64-70, 71-77, 78-84, 85-91, 92-98, > 98, and ≥ 7 , ≥ 14 , ≥ 28 , ≥ 42 , ≥ 56 , ≥ 70 , ≥ 84 , ≥ 98) of the duration (days) of treatment with the IMP will be determined.

Descriptive statistics of the mean daily dose will be determined for each section of the treatment period (1-7, 8-14, 15-21, 22-28, 29-35, 36-42, 43-49, 50-56, 57-63, 64-70, 71-77, 78-84, 85-91, 92-98, > 98) and for the entire treatment period.

Frequency distribution of the most frequent dose will be determined for each section of the treatment period (1-7, 8-14, 15-21, 22-28, 29-35, 36-42, 43-49, 50-56, 57-63, 64-70, 71-77, 78-84, 85-91, 92-98, > 98) and for the entire treatment period. Frequency distribution of the final dose will also be determined.

9.2 Adverse Events

Adverse events will be coded using Medical Dictionary for Regulatory Activities (MedDRA) (Ver. 25.0). The incidences of the following events will be summarized according to System Organ Class (SOC) and Preferred Term (PT). If an AE occurs more than once in the same subject, the severest event will be used in summarization.

- Adverse events occurring after initiation of IMP administration (treatment-emergent adverse events [TEAEs])
- TEAEs by severity
- TEAEs with an outcome of death
- Serious TEAEs
- TEAEs leading to discontinuation of the IMP
- TEAEs leading to IMP dose reduction
- TEAEs occurring in $\geq 2\%$ of subjects in any group

- TEAEs by days of initial onset (1-7, 8-14, 15-21, 22-28, 29-35, 36-42, 43-49, 50-56, 57-63, 64-70, 71-77, 78-84, 85-91, 92-98, > 98, post-trial treatment).

TEAEs potentially causally related to the IMP will also be summarized in the same manner.

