6.6 Safety Analysis

Safety analysis will be performed using the safety analysis set. Baseline is defined as the last data obtained prior to initiation of IMP treatment in this trial.

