3.2 Trial Treatments

Brexipiprazole will be administered orally as one tablet once a day for 14 weeks. Although the temporal relationship between IMP administration and meals will not be considered, subjects should take the IMP at the specified time in so far as possible. The IMP doses are shown in Table 3.2-1. IMP administration will be initiated at 0.5 mg and the dose will be increased to 1 mg after evaluation at Week 1 (Day 8) and to 2 mg after evaluation at Week 2 (Day 15). If the investigator or subinvestigator judges that dose increase to 2 mg is difficult for safety reasons based on the subject's condition after evaluation at Week 2 (Day 15), the dose may be maintained at 1 mg (see [Section 3.2 1](#) Dose Maintenance at 1 mg). From Week 2 (Day 15), the dose may be reduced or increased to 1 or 2 mg if the investigator or subinvestigator decides that dose adjustment is necessary (see [Section 3.2 2](#) Dose Change). In cases where dose reduction to lower than 1 mg is required, the trial should be discontinued.

Table 3.2-1 Doses of IMP		
Day 1-7	Day 8-14	Day 15-98
0.5 mg	1 mg	1 mg or 2 mg

1) Dose Maintenance at 1 mg

If the investigator or subinvestigator decides that dose increase to 2 mg is difficult due to the occurrence of an adverse event (AE) identified from the evaluation at Week 2 (Day 15), the dose will be maintained at 1 mg. The AE for which this judgement was made will be recorded in the case report form (CRF).

2) Dose Change

If the investigator or subinvestigator decides that dose adjustment is necessary based on the subject's condition, the dose will be reduced or increased to 1 or 2 mg.

If the investigator or subinvestigator decides that the current dose is not sufficiently effective, the dose will be increased to 2 mg. If either of the following cases applies, the dose will be reduced to 1 mg and the reason for dose reduction will be recorded in the CRF. In the event that both of the following cases apply, the AE should be recorded as the reason for dose reduction. When the occurrence of an AE necessitates dose reduction, enter "dose reduction" in the CRF as the action taken for the AE in relation to IMP administration.

The dose may be reduced to 1 mg in the following cases:

- Dose reduction is necessary because an AE has occurred.
- Dose reduction is necessary because symptoms have improved.

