Appendix 4 List of Summary Tables

- CT-8.2.1 Incidence of TEAEs by MedDRA System Organ Class and Preferred Term (Safety Analysis Set)
- CT-8.2.2 Incidence of Drug-related TEAEs by MedDRA System Organ Class and Preferred Term (Safety Analysis Set)
- CT-8.3.1 Incidence of TEAEs by MedDRA System Organ Class, Preferred Term and Severity (Safety Analysis Set)
- CT-8.3.2 Incidence of Drug-related TEAEs by MedDRA System Organ Class, Preferred Term and Severity (Safety Analysis Set)
- CT-8.4.1 Incidence of Deaths due to TEAEs by MedDRA System Organ Class and Preferred Term (Safety Analysis Set)
- CT-8.4.2 Incidence of Deaths due to Drug-related TEAEs by MedDRA System Organ Class and Preferred Term (Safety Analysis Set)
- CT-8.5.1 Incidence of Serious TEAEs by MedDRA System Organ Class and Preferred Term (Safety Analysis Set)
- CT-8.5.2 Incidence of Serious Drug-related TEAEs by MedDRA System Organ Class and Preferred Term (Safety Analysis Set)
- CT-8.6.1 Incidence of TEAEs Resulting in Discontinuation of IMP by MedDRA System Organ Class and Preferred Term (Safety Analysis Set)
- CT-8.6.2 Incidence of Drug-related TEAEs Resulting in Discontinuation of IMP by MedDRA System Organ Class and Preferred Term (Safety Analysis Set)
- CT-8.7.1 Incidence of TEAEs Resulting in Dose Reduction of IMP by MedDRA System Organ Class and Preferred Term (Safety Analysis Set)
- CT-8.7.2 Incidence of Drug-related TEAEs Resulting in Dose Reduction of IMP by MedDRA System Organ Class and Preferred Term (Safety Analysis Set)
- CT-8.8.1 Incidence of TEAEs of at Least 2% in Any Group by MedDRA System Organ Class and Preferred Term (Safety Analysis Set)
- CT-8.8.2 Incidence of Drug-related TEAEs of at Least 2% in Any Group by MedDRA System Organ Class and Preferred Term (Safety Analysis Set)
- CT-8.9.1 Incidence of TEAEs by MedDRA System Organ Class, Preferred Term and Time to First Onset (Safety Analysis Set)
- CT-8.9.2 Incidence of Drug-related TEAEs by MedDRA System Organ Class, Preferred Term and Time to First Onset (Safety Analysis Set)
- CT-8.10.1 Incidence of TEAEs for EPS (Safety Analysis Set)
- CT-8.10.2 Incidence of TEAEs for Accidents and Injuries Including Fall (Safety Analysis Set)
- CT-8.10.3 Incidence of TEAEs for Cerebrovascular Events (Safety Analysis Set)
- CT-8.10.4 Incidence of TEAEs for Cardiovascular Events (Safety Analysis Set)
- CT-8.10.5 Incidence of TEAEs for Effect on Glucose (Safety Analysis Set)

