- CT-9.3 Listing of Discontinuation of IMP due to Adverse Events (Safety Analysis Set)
- CT-9.4 Listing of Dose Reduction due to Adverse Events (Safety Analysis Set)
- CT-10.1.1 Mean Change From Baseline in Clinical Laboratory Test Results - Serum Chemistry (Safety Analysis Set)
- CT-10.1.2 Mean Change From Baseline in Clinical Laboratory Test Results - Hematology (Safety Analysis Set)
- CT-10.1.3 Mean Change From Baseline in Clinical Laboratory Test Results - Urinalysis (Safety Analysis Set)
- CT-10.1.4 Mean Change From Baseline in Clinical Laboratory Test Results - Prolactin, by Gender (Safety Analysis Set)
- CT-10.1.5 Mean Change From Baseline in Clinical Laboratory Test Results - Other Tests (Safety Analysis Set)
- CT-10.2.1 Shift Tables of Clinical Laboratory Test Results - Serum Chemistry (Safety Analysis Set)
- CT-10.2.2 Shift Tables of Clinical Laboratory Test Results - Hematology (Safety Analysis Set)
- CT-10.2.3 Shift Tables of Clinical Laboratory Test Results - Urinalysis1 (Safety Analysis Set)
- CT-10.2.4 Shift Tables of Clinical Laboratory Test Results - Urinalysis2 (Safety Analysis Set)
- CT-10.2.5 Shift Tables of Clinical Laboratory Test Results - Prolactin, by Gender (Safety Analysis Set)
- CT-10.2.6 Shift Tables of Clinical Laboratory Test Results - Other Tests (Safety Analysis Set)
- CT-10.3.1 Incidence of Laboratory Test Values With Potential Clinical Relevance (Safety Analysis Set)
- CT-10.3.2 Listing of Laboratory Test Values With Potential Clinical Relevance by Subject (Safety Analysis Set)
- CT-10.4.1 Incidence of Potential Hy's Law Cases (Safety Analysis Set)
- CT-10.4.2 Listing of Potential Hy's Law Cases (Safety Analysis Set)
- CT-10.5.1 Incidence of Laboratory Test Values With Potential Clinical Relevance - Prolactin (Safety Analysis Set)
- CT-10.5.2 Listing of Laboratory Test Values With Potential Clinical Relevance - Prolactin (Safety Analysis Set)
- CT-10.6.1 Incidence of Treatment-emergent Significant Change in Lipids (Safety Analysis Set)
- CT-10.6.2 Listing of Treatment-emergent Significant Change in Lipids (Safety Analysis Set)

CT-10.7.1 Incidence of Treatment-emergent Significant Change in Glucose (Safety Analysis Set)
CT-10.7.2 Listing of Treatment-emergent Significant Change in Glucose (Safety Analysis Set)
CT-11.1 Mean Change From Baseline in Vital Signs (Safety Analysis Set)
CT-11.2 Incidence of Potentially Clinically Relevant Abnormalities in Vital Signs (Safety Analysis Set)

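### Does the SAP need a separate table of adverse events that kept subjects at 1 mg?

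*SAP*

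**What the plan says.** Protocol 3.2.1 and SAP 3.2 describe two ways in which an adverse event can change the dose.

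- **Hold.** The dose goes to 2 mg after the Week 2 evaluation unless an event makes that difficult, in which case it stays at 1 mg. "The AE for which this judgement was made will be recorded in the case report form (CRF".
- **Reduction.** A subject on 2 mg may go down to 1 mg because of an event or because symptoms improved. When an event is the cause, dose reduction is entered "in the CRF as the action taken for the AE in relation to IMP administration".

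There is no lower step: "In cases where dose reduction to lower than 1 mg is required, the trial should be discontinued".

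On the reporting side, SAP 9.2 lists "TEAEs leading to IMP dose reduction" and events leading to discontinuation, and Protocol 6.6.1 has the same two dose-related categories. Appendix 4 carries them into CT-8.7.1, "Incidence of TEAEs Resulting in Dose Reduction of IMP by MedDRA System Organ Class and Preferred Term (Safety Analysis Set", and CT-9.4, "Listing of Dose Reduction due to Adverse Events (Safety Analysis Set". The denominator is set by Protocol 6.6: "Safety analysis will be performed using the safety analysis set". SAP 9.1 separately covers dosing: "Frequency distribution of the most frequent dose will be determined for each section of the treatment period", with Days 15-21 as one of the sections. SAP 5 has analyses produced for brexpiprazole rollovers, placebo rollovers and all subjects unless otherwise specified.

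**The concern.** Safety is the main objective, 2 mg is the default step at Week 2, and the hold is the safety exception to it. The plan collects the reason for the hold and then specifies no summary of it. A reader who takes CT-8.7 as the measure of event-driven dose changes would miss every subject held at 1 mg and never raised.

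The two rollover groups make this look more serious. Protocol 3.2.2 notes that placebo rollovers had no brexpiprazole in the parent trial, so their hold rate may differ from that of brexpiprazole rollovers. If it does, CT-8.7 cannot show it. The group with the larger share never reaching 2 mg could even show the lower reduction rate, simply because fewer of its subjects are at risk of a reduction.

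**Working it through.** **1. Group sizes.** The sample-size sections (Protocol 6.1, SAP 4) give 100 brexpiprazole completers and a 3:4:4 allocation (1 mg, 2 mg, placebo). The total is 100 × (3+4+4)/(3+4) = 157.1, which reproduces the stated 157. The split is 157 × 7/11 = 99.9 and 157 × 4/11 = 57.1, so about 100 and 57.

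**2. Who can enter CT-8.7.** A need to go below 1 mg means discontinuation, so a reduction must start from 2 mg. A held subject enters only if later raised to 2 mg and then reduced. This part of the concern is right.

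**3. How much CT-8.7 could leave out.** The documents give no hold or reduction rate. Assume that held subjects are never raised and that 10% of the others are reduced:

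| Assumed hold rate | Held (of 157) | Reduced (10% of the rest) | Share of held-or-reduced shown in CT-8.7 |
|---|---|---|---|
| 5% | 8 | 149 × 0.10 ≈ 15 | 15/23 = 65% |
| 10% | 16 | 141 × 0.10 ≈ 14 | 14/30 = 47% |
| 20% | 31 | 126 × 0.10 ≈ 13 | 13/44 = 30% |

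If nobody is held, nothing is left out. By group, one CT-8.7 result of 10/100 = 10.0% against 6/57 = 10.5% fits several totals. With 5 brexpiprazole rollovers held, the brexpiprazole total is 15/100 = 15.0%. With 3, 6 or 14 placebo rollovers held, the placebo total is 9/57 = 15.8%, 12/57 = 21.1% or 20/57 = 35.1%.

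**4. Whether the holds are visible elsewhere.** The natural objection to SAP 9.1 is that 1 mg can mean a hold, an event-led reduction or a reduction after improvement. That is fair for later weeks but much weaker for Days 15-21:

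- Safety is the only stated reason for not going to 2 mg at Week 2, and item 1 of SAP 3.2 ties it to an adverse event.
- Both kinds of reduction require 2 mg first, and the next scheduled visit is Week 4 (Day 29, window Day 27-31).
- The Week 2 window is Day 13-17 (Protocol Table 3.8-2). Even with a visit on Day 17 and the first 2 mg dose on Day 18, a subject who is raised takes 2 mg on Days 18-21 (4 days) and 1 mg on Days 15-17 (3 days). The most frequent dose is still 2 mg.

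A most frequent dose of 1 mg in Days 15-21 therefore means a hold, apart from a reduction within about three days of the increase, a visit outside its window, missed doses after a late visit, or an exit early in that week. The table is produced by rollover group. With 14/57 and 5/100 held, it would show about 24.6% against 5.0% at 1 mg.

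**5. What else is planned.** Held subjects' treatment-emergent events count in CT-8.2 (all events), CT-8.3 (severity) and CT-8.9 (time to onset, including Days 1-7 and 8-14). Appendix 5 plans listing AE-1 for adverse events and SMED-1 for study medication.

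**6. What remains.** No table in the available text, which for Appendix 4 begins at CT-8.2.1, gives the system organ class and preferred term of the event behind each hold.

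**The case for a change.** The strongest case for a change is that the Week 2 hold is the first planned point at which an event alters the dose, that its cause is collected deliberately, and that a table and a listing would report it without touching CT-8.7 or the dosing. Agreement between SAP 9.2 and Protocol 6.6.1 shows only that the omission is shared. All of that stands, as does the fact that no planned summary names the events.

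The claim of a hidden group difference does not stand, because SAP 9.1 would largely show it. The reversal is also weak evidence of harm. Take 5 against 14 held and 10 against 5 reduced. CT-8.7 then reads 10.0% against 5/57 = 8.8%, a difference of -1.2 points (Newcombe 95% CI -10.2 to 9.9), while held-or-reduced is 15.0% against 19/57 = 33.3%. An interval that wide shows no order to misread, and one more placebo-rollover reduction (6/57 = 10.5%) removes the reversal.

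Nor would the extra table be complete. Adverse events are collected from the parent trial's Week 10 evaluation, up to 10 days before dosing, and parent-trial events that did not worsen are not adverse events here (Protocol 5.1, 5.2). A hold for either would not count as a treatment-emergent event. SAP 9.2 repeats its summaries for drug-related events, so the work would roughly double. The CRF is not in the documents, so it is also unknown whether the hold reason is a coded field.

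**Conclusion.** No change to the plan is needed. The omission is real, but no stated number, rule or conclusion is wrong because of it. CT-8.7 reports dose reductions, as titled, and the SAP delivers the dose-related categories that Protocol 6.6.1 sets out. Neither document promises a combined summary of dose modification, and 1 mg is a planned dose from Day 15.

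The size of the gap cannot be derived from the documents. At assumed hold rates of 5% to 20%, 8 to 31 of 157 subjects would be outside CT-8.7, but their number by group would be largely readable from the Days 15-21 dose distribution. Their treatment-emergent events would still be counted in the overall tables. SAP 6 names no primary or secondary outcome, the trial is uncontrolled and the summaries are descriptive, so no between-group inference rests on CT-8.7.

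What is left is a table that some readers would like, naming the events behind the holds. Analysts can produce it on request if the CRF field is usable. The conclusion rests on two readings: that safety is the only stated route to staying at 1 mg at Week 2, and that the SAP 9.1 tables are produced by rollover group, as SAP 5 provides.

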9.2.1 Adverse Events of Interest

Each AE of interest is defined in Appendix 4 in the Statistical Analysis Plan for the double-blind trial (331-102-00088). Numbers and proportions of subjects with the following AEs of interest will be summarized by SOC and PT.

- Extrapyramidal AEs
- Accident- and injury-related AEs
- Cerebrovascular AEs
- Cardiovascular AEs
- Glucose metabolism-related AEs
- Lipid metabolism-related AEs
- Body weight-related AEs
- Blood disorder-related AEs
- Hypersensitive symptom-related AEs
- Neuroleptic malignant syndrome-related AEs
- Orthostatic disorder-related AEs
- Prolactin increase-related AEs
- QT interval prolongation-related AEs
- Rhabdomyolysis
- Seizure-related AEs
- Oversedation-related AEs
- Suicide/suicide attempt-related AEs
- Venous thrombosis
- Infectious pneumonia

9.2.2 Subgroup Analysis of Adverse Events

Numbers and proportions of subjects with TEAEs will be summarized by SOC and PT in each of the following subgroups. Subgroups of medical care category and subgroups of type of caregiver will include only subjects for whom the medical care category or the type of caregiver remains unchanged throughout the trial.

- Medical care category (inpatient, outpatient)

- Prior use of antipsychotics (yes or no)
- Type of caregiver (hospital staff, care facility staff, family, or other)
- Sex (male, female)
- Age ($< 80, \geq 80$) ($< 65, \geq 65$ to $< 75, \geq 75$)
- Body weight (\leq median, $>$ median)
- BMI (\leq median, $>$ median)
- Impact of COVID-19 pandemic (subjects who completed/discontinued the trial before 07 Apr 2020, subjects who completed/discontinued the trial on or after 07 Apr 2020)
- Concomitant use of antidementia drugs (yes or no)

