3.5 Requirements for Caregivers

A caregiver who meets the following criteria will be designated as the main caregiver in the trial:

- Is able to obtain the patient information required for evaluation (24-hour information wherever possible on the patient's activities including toilet use, eating, bathing, changing, and other daily activities) during the trial period and provide this information during the inquiries on trial evaluation items; and
- Provides the patient with care and can observe the patient's condition in at least 4 days per week for 4 hours or more a day, until the completion of the examinations scheduled at the completion or discontinuation of IMP administration.

If there are multiple caregivers in charge of the patient's care, the main caregiver will not only provide patient information from his or her own observations but also obtain from the other caregivers information on the patient's condition during those periods when the patient was not under his or her observation and provide all patient information required for evaluations during the inquiries on the trial evaluation items.

If the main caregiver is unable to respond to queries, a substitute caregiver is allowed to respond to queries on the trial evaluation items. A substitute caregiver should be able to obtain basic patient information required for evaluations from other caregivers and provide the same information as would have been provided by the main caregiver during inquiries on the trial evaluation items, and should be selected from among the caregivers in charge of the patient's care. Patient information required for evaluations should be collected until the end of follow-up observation period, which is 28 days after the completion or discontinuation of IMP administration. Queries at the end of follow-up observation period will be answered not only by the main caregiver but also by caregivers who are in charge of the patient's care and able to provide the patient information required for evaluations.

In the event that replacement of the main caregiver is required during the trial period due to a change in the patient care environment or for other reasons, a caregiver who is able to provide the patient information required for evaluations in response to queries regarding the trial evaluation items will be selected as the new main caregiver. The new main caregiver must also be able to observe the patient's condition in at least 4 days per week for 4 hours or more a day.

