3.9.3.2 Documenting Reasons for Discontinuation

All subjects have the right to withdraw, and the investigator or subinvestigator can discontinue a subject's participation in the trial at any time if medically necessary. In

addition, subjects meeting the following criteria must be withdrawn from the trial. Only one main reason for discontinuation will be recorded in the CRF.

- Adverse event
 - Death
 - Continuation of IMP would place the subject at undue risk, as determined by the investigator or subinvestigator (eg, there is a safety concern possibly, probably, or likely related to IMP).
 - SAE
 - The dose of brexpiprazole needs to be reduced to lower than 1 mg due to the occurrence of an AE.
 - The subject experiences worsening of agitation, and the investigator or subinvestigator judges that the subject should be withdrawn from the trial (worsening of agitation is to be reported as an AE).
 - The subject decides to discontinue the treatment because of annoyance or discomfort due to a nonserious AE that is not otherwise determined to be an undue hazard.
- Subjects becoming bedridden and requiring assistance for excretion, eating, and changing clothes
- Subject's withdrawal of informed consent
- Legally acceptable representative's withdrawal of informed consent
- Caregiver's withdrawal of informed consent
- Marked noncompliance with the IMP regimen (compliance rate of < 65% during the interval between the previous date of compliance verification and the current date of compliance verification)
- Protocol deviation (other than marked noncompliance with the IMP regimen)
 - The subject is discovered to have not met the inclusion/exclusion criteria.
 - The subject has received any prohibited concomitant drugs or is judged to be in need of prohibited drugs.
- Lost to follow-up
- Lack of efficacy
- Pregnancy (see [Section 5.5 Pregnancy](#))
- Termination of all or part of the trial by the sponsor
- Investigator or subinvestigator's judgment (for reasons other than occurrence of AE)
- Other
 - After initiation of IMP treatment, any of the following external test results at Week 10 of Trial 331-102-00088 are obtained:
 - QTcF on the basis of ECG results from the central ECG laboratory is ≥ 450 msec in men or ≥ 470 msec in women (in triplicate ECG examinations, at least 2 measurements meet the criteria).

- Results from the central laboratory:
 - Platelet count: $\leq 75,000/\text{mm}^3$
 - Hemoglobin: $\leq 9 \text{ g/dL}$

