5.1 Definitions

An AE is defined as any untoward medical occurrence in a patient or clinical trial subject administered a medicinal product and which does not necessarily have a causal relationship with this treatment. Adverse events would not include events recorded as complications at screening of Trial 331-102-00088 for which the underlying condition was known and no worsening occurred during this trial. In addition, events that were recorded as AEs before evaluation at Week 10 of Trial 331-102-00088 and did not worsen during this trial (331-102-00184) will not be deemed to be AEs in this trial. An adverse drug reaction is any untoward and unintended response to an IMP related to any dose administered.

A suspected adverse reaction is any AE for which there is a reasonable possibility that the IMP caused the AE. For the purpose of Investigational New Drug safety reporting, “reasonable possibility” means there is evidence to suggest a causal relationship between the IMP and the AE. Suspected adverse reaction implies a lesser degree of certainty about causality.

An SAE includes any event that results in any of the following outcomes:

- Death
- Life-threatening; ie, the subject was, in the opinion of the investigator or subinvestigator, at immediate risk of death from the event as it occurred. It does not include an event that, had it occurred in a more severe form, might have caused death.
- Persistent or significant incapacity/disability or substantial disruption of the ability to conduct normal life functions.
- Requires inpatient hospitalization or prolongs hospitalization
 - Hospitalization itself should not be reported as an SAE; whenever possible the reason for the hospitalization should be reported.
 - Hospitalizations or prolonged hospitalizations for social admissions (ie, those required for reasons of convenience or other nonmedical need) are not considered SAEs.
- Congenital anomaly/birth defect.
- Other medically significant events that, based upon appropriate medical judgment, may jeopardize the subject and may require medical or surgical intervention to prevent one of the outcomes listed above, eg, allergic bronchospasm requiring intensive treatment in an emergency room or home, blood dyscrasias or convulsions that do not result in hospitalization, or the development of drug dependency or drug abuse.

Nonserious AEs are all AEs that do not meet the criteria for a “serious” AE.

Immediately Reportable Event (IRE):

- Any SAE

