- CT-8.10.6 Incidence of TEAEs for Effect on Lipids (Safety Analysis Set)
- CT-8.10.7 Incidence of TEAEs for Effect on Weight (Safety Analysis Set)
- CT-8.10.8 Incidence of TEAEs for Haematopoietic/Leukopenia (Safety Analysis Set)
- CT-8.10.9 Incidence of TEAEs for Hypersensitivity (Safety Analysis Set)
- CT-8.10.10 Incidence of TEAEs for Neuroleptic Malignant Syndrome (Safety Analysis Set)
- CT-8.10.11 Incidence of TEAEs for Orthostatic Hypotension, Dizziness, and Syncope (Safety Analysis Set)
- CT-8.10.12 Incidence of TEAEs for Effect on Prolactin (Safety Analysis Set)
- CT-8.10.13 Incidence of TEAEs for QT Prolongation (Safety Analysis Set)
- CT-8.10.14 Incidence of TEAEs for Rhabdomyolysis and CPK Elevation (Safety Analysis Set)
- CT-8.10.15 Incidence of TEAEs for Seizures (Safety Analysis Set)
- CT-8.10.16 Incidence of TEAEs for Somnolence (Safety Analysis Set)
- CT-8.10.17 Incidence of TEAEs for Suicidality (Safety Analysis Set)
- CT-8.10.18 Incidence of TEAEs for VTE (Thrombotic and Embolic Events) (Safety Analysis Set)
- CT-8.10.19 Incidence of TEAEs for Infective Pneumonia (Safety Analysis Set)

- CT-8.11.1 Incidence of TEAEs by MedDRA System Organ Class and Preferred Term by Medical Care Category (Safety Analysis Set)
- CT-8.11.2 Incidence of TEAEs by MedDRA System Organ Class and Preferred Term by Prior Antipsychotics (Safety Analysis Set)
- CT-8.11.3 Incidence of TEAEs by MedDRA System Organ Class and Preferred Term by Main Care Giver (Safety Analysis Set)
- CT-8.11.4 Incidence of TEAEs by MedDRA System Organ Class and Preferred Term by Gender (Safety Analysis Set)
- CT-8.11.5.1 Incidence of TEAEs by MedDRA System Organ Class and Preferred Term by Age(< 80, >= 80) (Safety Analysis Set)
- CT-8.11.5.2 Incidence of TEAEs by MedDRA System Organ Class and Preferred Term by Age(<65, >=65 - <75, >=75) (Safety Analysis Set)
- CT-8.11.6 Incidence of TEAEs by MedDRA System Organ Class and Preferred Term by Baseline Weight (Safety Analysis Set)
- CT-8.11.7 Incidence of TEAEs by MedDRA System Organ Class and Preferred Term by Baseline BMI (Safety Analysis Set)
- CT-8.11.8 Incidence of TEAEs by MedDRA System Organ Class and Preferred Term by Impact of COVID-19 Pandemic (Safety Analysis Set)
- CT-8.11.9 Incidence of TEAEs by MedDRA System Organ Class and Preferred Term by Concomitant Antidementia Drugs (Safety Analysis Set)
- CT-9.1 Listing of Deaths (Safety Analysis Set)
- CT-9.2 Listing of Serious Adverse Events (Safety Analysis Set)

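### TEAE tables by care category and caregiver drop subjects whose status changed, so an admission caused by a TEAE can remove that subject from the table

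*SAP*

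**What the plan says.** SAP 9.2.2 lists the subgroups in which TEAEs are tabulated by system organ class and preferred term. For two of them, medical care category (inpatient, outpatient) and type of caregiver (hospital staff, care facility staff, family, other), it adds that the subgroups "will include only subjects for whom the medical care category or the type of caregiver remains unchanged throughout the trial". The output is CT-8.11.1 and CT-8.11.3 in SAP Appendix 4. Both titles name the safety analysis set and neither mentions the restriction.

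Other parts of the plan bear on this rule:

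- **Recording of changes.** Protocol 3.8.1.3 has the investigator record the date, care category and caregiver type whenever the subject's environment changes, from the baseline evaluation to Week 14. It makes no exception for a temporary or AE-related admission.
- **Caregiver.** Protocol 3.5 foresees the case in which "replacement of the main caregiver is required during the trial period due to a change in the patient care environment".
- **Admission as an SAE.** Protocol 5.1 includes this seriousness criterion: "Requires inpatient hospitalization or prolongs hospitalization".
- **Withdrawal.** Protocol 3.9.3.2 states that "subjects meeting the following criteria must be withdrawn from the trial", and SAE is on that list.
- **Start-of-trial status.** SAP 7.3, footnote b, takes care category and caregiver type at the start of this trial for the baseline table.
- **Weight and BMI.** In the same family of tables, CT-8.11.6 and CT-8.11.7 group these time-varying measures by baseline value.

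**The concern.** A subgroup for a safety table should be fixed by something the adverse event cannot alter. Here it is not. An outpatient who falls, develops pneumonia or becomes oversedated and is admitted may be recorded as having moved from outpatient to inpatient. Under the rule that subject is then in neither stratum, and the event that caused the move disappears from the table along with the subject. The terms most exposed are those that lead to admission, which are also the ones a reader comparing care settings would look for.

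Evaluating safety is this trial's main objective, and CT-8.11.1 and CT-8.11.3 are the TEAE summaries listed by care setting and by caregiver. A low outpatient rate for a term that causes admission could be read as reassuring when it partly reflects who was left out. Nothing in the table title would alert the reader.

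**Working it through.** **The plan's own figure.** The only related planning number is the sample size (Protocol 6.1, SAP 4). With 3:4:4 allocation, 7/11 of subjects come from brexpiprazole, so 100 / (7/11) = 157.14, or 157. The figure reproduces and is not in dispute. The expected split of 157 is 157 × 7/11 = 99.9 from brexpiprazole and 157 × 4/11 = 57.1 from placebo.

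**Formula.** In one stratum defined at the start of the trial, let N be the number of subjects, k the number with the term, a the number of those k recorded as changers, and c the number of changers without the term. Grouped by starting status the table shows k/N. Under SAP 9.2.2 it shows

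(k − a) / (N − a − c).

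The two are equal when c = a(N − k)/k. Below that value of c the term is understated, and above it overstated.

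**Inputs.** The documents give no outpatient, admission or TEAE counts, so every N, k, a and c below is assumed.

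*Preferred term, N = 120 outpatients, k = 6 (true 5.0%)*

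| a | c = 0 | c = 10 | Break-even c = a × 114/6 |
|---|---|---|---|
| 0 | 6/120 = 5.0% | 6/110 = 5.5% | 0 |
| 1 | 5/119 = 4.2% | 5/109 = 4.6% | 19 |
| 2 | 4/118 = 3.4% | 4/108 = 3.7% | 38 |
| 3 | 3/117 = 2.6% | 3/107 = 2.8% | 57 |
| 6 | 0/114 = 0% | 0/104 = 0% | none (all cases removed) |

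Check of the break-even for a = 1: 5/(120 − 1 − 19) = 5/100 = 5.0%.

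*Smaller group, N = 75 outpatients among the roughly 100 ex-brexpiprazole subjects, k = 3 (true 4.0%), c = 0*

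- a = 0: 3/75 = 4.0%
- a = 1: 2/74 = 2.7%, break-even c = 1 × 72/3 = 24
- a = 2: 1/73 = 1.4%, break-even c = 48
- a = 3: 0/72 = 0%

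*Any TEAE, N = 120, k = 70 (true 58.3%)*

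- a = 6, c = 0: 64/114 = 56.1%
- a = 6, c = 6: 64/108 = 59.3%
- break-even c = 6 × 50/70 = 4.3

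For the any-TEAE row the effect is about two points down or one point up. For a single term that leads to admission it can be a large share of the true rate.

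**The inpatient side.** Inpatients discharged during the trial are also removed. If a proportion d is discharged and none of them had a TEAE, a true rate p is shown as p/(1 − d). With p = 50%, that is 52.6% for d = 5% and 55.6% for d = 10%. The contrast between settings can therefore be distorted from both sides.

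**Where the rule is not settled by the text.**

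- SAP 9.2.2 requires no change throughout the trial. The trial period runs to the end of follow-up (SAP 3.1), but changes are recorded only to Week 14 (Protocol 3.8.1.3).
- No passage says whether an acute admission, one that coincides with withdrawal, or one in follow-up is a change.
- Protocol 3.8.1.3 splits outpatients into institutionalised and home care, while the SAP subgroup has only inpatient and outpatient. Whether a move within outpatient care counts is not stated.
- The wording joins the two variables with an or, so it is not certain that each table applies only its own variable.

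**The case against.** The strongest objection concerns withdrawal. An AE that requires admission is an SAE, and SAE is a listed withdrawal criterion. On the protocol's own terms, the outpatient who is admitted for a TEAE and carries on as a recorded changer is not the expected case. Many changers who stay in the trial would be social admissions, discharges or caregiver replacements, and dropping those without the term raises the displayed rate. This stands as a limit on size and direction. It does not remove the problem: withdrawal does not prevent the admission from being recorded as a change, and inclusion would then depend on how a site handled the entry around withdrawal.

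A second objection is that TEAEs among people in one constant setting are a legitimate, prespecified target, and that grouping by starting status attributes events after a move to the wrong setting. Both parts are fair. They support keeping the restricted table as a labelled secondary view. They do not support making it the only one, since its exclusions can be caused by the outcome being counted.

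The comparison with weight and BMI is only supportive. Those are continuous and split at the median, so being unchanged has no natural meaning for them. The same list also has a COVID-19 subgroup defined by date of completion or discontinuation, which is itself after baseline.

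Finally, the overall, serious, death, discontinuation, time-to-onset and AE-of-interest tables and the listings keep every subject. No event is lost from the report as a whole. That is why the point is minor.

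**Conclusion.** The concern holds, as a minor point. SAP 9.2.2 makes membership of two TEAE tables depend on post-baseline status that a TEAE can change, and the recording rule in Protocol 3.8.1.3 has no exception that would prevent it. The bias arises only if an admission for a TEAE is recorded as a change and, for the caregiver table, only if caregiver type changes too.

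The size cannot be determined from the documents and may be nil. Under the assumed counts, a 5.0% term in the outpatient stratum would show anywhere from 5.5% down to 0%, with understatement whenever at least one admitted case is recorded and changers without the term number fewer than 19 per recorded case. The any-TEAE rate moves by only a point or two in either direction. CT-8.11.1 and CT-8.11.3 are the only tables affected. The Patient Care listing (PDATA-6) may let a reader identify changers, but its content is not described.

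**What to change.** In SAP 9.2.2, define both subgroups by care category and caregiver type at the start of this trial, as SAP 7.3 footnote b already does, and include every subject in the safety analysis set. Add a footnote to CT-8.11.1 and CT-8.11.3 giving the number of changers in each stratum.

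If TEAEs in a constant setting are of interest, keep the unchanged-only version as a sensitivity table labelled as a restricted population. For that version, state:

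- whether acute admissions count as a change, including those that coincide with withdrawal or fall in follow-up;
- whether a move between institution and home counts within outpatient;
- that each table applies only its own variable, if that is the intention.

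The cost is one or two SAP sentences and a table footnote. The data are already collected and no protocol amendment is needed. The drawback is that events after a move are attributed to the starting setting; the count of changers shows how much that could matter.
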